8.3.5 Serious Adverse Device Effect Reporting

In the occurrence of a SADE, expedited reporting requirements are followed. The AE eCRF page should be completed within 24 h of awareness of the event. The Investigator needs to follow-up on all ongoing SADEs until resolution. In case of a break-down of the eCRF system, an SAE/SADE Report Form needs to be completed for each event and sent to the sponsor within 24 h of awareness of the event:

Contact address:

Clinical Research, Institut Straumann AG

[contact] [contact]

Email: [contact]

The product safety officer at Straumann will work with the Investigator to determine whether the event is anticipated (ASADE) or unanticipated (USADE). In case of USADE, the Investigator must promptly notify its reviewing EC as soon as possible, but no later than 10 working days after 1st learning of the event.

Since this is a multi-center study, Straumann will inform the Investigators at all participating centers of any reported USADEs related to this protocol and the study device. Copies of such external USADE reports should be forwarded to the EC for review and a copy must be kept in the Investigator Site Files.

8.3.6 Additional Safety Reporting

Straumann will report additional safety information to the centers that is relevant to the protocol or study device and may affect the risk/benefit ratio, the rights, safety or welfare of patients, or the integrity of the study. Such reports may include notification of any changes to the IfU (Annex 1), any publications or interim reports, or any product recalls.

8.4 Monitoring of Patients with Adverse Events

Any AE that occurs during the course of this study must be monitored and followed-up by the Investigator until one or more of the following have occurred:

- The AE is resolved,
- Pathological laboratory findings have returned to normal,
- Steady state has been achieved, or
- It has been shown to be unrelated to the study devices.

The outcome of an event will be pursued until resolution or until the last data queries are issued following the patient's last study visit. For screening failures, ongoing AEs, ADEs and DDs must be followed and updated until the date the patient is deemed a screening failure. For patient documented as lost to follow-up, ongoing AEs, ADEs, and DDs will not be followed.

It is the responsibility of the sponsor to cooperate with the Investigator to assure that any necessary additional therapeutic measures and follow-up procedures are performed.

8.5 Pregnancy

If a female patient becomes pregnant during the course of the study, the study visits should be completed as scheduled. Any study assessments that could potentially interfere with the pregnancy should be avoided until after the pregnancy (e.g., radiographs, etc.). The pregnancy should be recorded as an AE, whereas the start of pregnancy will be recorded as the start date of the AE and the date of child birth will be recorded as the end date. Furthermore, the outcome of the pregnancy should be documented.

9 Statistical Considerations

A qualified statistician will perform all statistical analyses.

Since the purpose of this study is descriptive, there are no formal sample size calculations based on comparative hypothesis testing. Statistical analyses will be descriptive (e.g., reporting means, standard deviations, medians, minima, and maxima for continuous variables and patient counts, frequencies and percentages for categorical variables).

The primary analysis will be conducted after all patients completed the 12-month Follow-Up Visit. Baseline is implant placement.

9.1 Analysis populations (Data Sets)

The following analysis sets are planned for this study:

9.1.1 Safety Data Set

The safety analysis set (SAS) consists of all patients in the study, who received the study implant. The SAS population will be the basis for the safety analysis.

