3.4.2 Secondary Endpoints

The following parameters will be measured as secondary endpoints:

- PES at 6 months after implant placement
- Implant success at 12 months after implant placement
- · Marginal bone level changes at 12 months after implant placement
- AEs and ADEs incidence

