8.2.2 Relationship to the Study Device or Procedure

It is useful to analyze an AE in accordance with the time of its occurrence and the surgery date (i.e., during the implantation period of the device, application, or attempt of placement).

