8.3 Procedure for Reporting Adverse Events and Device Deficiencies

Adverse Event reporting will begin at the start of implant placement at the Baseline Visit until the last protocol-specific procedure of a patient. All AE/SAEs should be collected, fully investigated and documented in the source document and appropriate eCRF pages for all patients. In the eCRF, only 1 AE/SAE eCRF entry should be completed per event. To ensure patient confidentiality, the reports in Sections 8.3.1 to 8.3.6 will include the patient number only.

The report sequence "initial" shall be ticked on the eCRF page for the initial AE report. In order to capture the new information, the AE eCRF page shall be updated and the report sequence "follow-up" or "final" shall be ticked as appropriate.

Adverse Events like swelling, pain or bleeding do not need to be captured on the eCRF page as long as they occur in the same or milder intensity as during standard treatment during the following procedures:

- Visit 2: implant placement
- Visit 3: suture removal
- Visit 4: Placing of the provisional crown
- Visit 5: Placing of the final crown

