9.1.2 Full analysis set

The full analysis set (FAS) consists of all patients in the study, who received the study implant and from whom at least one follow-up measurement after baseline is available. This analysis will include patients regardless of any protocol deviations and/or premature termination. The primary analysis will be performed by the intent-to-treat principle with the FAS.

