11.3.4 Screening Failures

Any patient that has signed the Informed Consent Form and does not receive the study device is considered a screening failure. In the event of a screening failure, the eCRF page should be completed up to the visit when the patient was determined to be a screening failure. The Study Termination eCRF page should also be completed.

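### Reportable ADEs in patients whose implant placement is started but who do not receive the implant have no place in the planned ADE incidence

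*Combined protocol and SAP*

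**What the plan says.** - **Analysis set.** Section 9.1.1: "The safety analysis set (SAS) consists of all patients in the study, who received the study implant". The same section makes this set the basis of the safety analysis. Section 9.1 defines two further sets, the full analysis set and the per-protocol set, and both also require receipt of the implant.
- **Endpoint.** Section 3.4.2 lists "AEs and ADEs incidence" as a secondary endpoint.
- **Start of collection.** Section 8.3: "Adverse Event reporting will begin at the start of implant placement at the Baseline Visit". The trigger is the start of placement, not its completion. Section 8.1.4 counts events related to the procedure, surgery included, as ADEs.
- **Screening failure.** Section 11.3.4: "Any patient that has signed the Informed Consent Form and does not receive the study device is considered a screening failure". For such a patient, "the eCRF page should be completed up to the visit when the patient was determined to be a screening failure". Section 3.7 treats a patient as enrolled only once the implant has been received.
- **Safety data in screening failures.** Section 8.4: "For screening failures, ongoing AEs, ADEs and DDs must be followed and updated until the date the patient is deemed a screening failure".
- **Attempted placement.** Section 8.2.2 advises judging an AE against the time of surgery, described as "during the implantation period of the device, application, or attempt of placement".

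**The concern.** The rule for collecting events and the rule for analysing them use different starting points. Collection opens when surgery opens. Analysis admits a patient only if the implant was received. A patient can fall between the two: surgery is started, a reportable event occurs, and the patient leaves without having received the implant.

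Such a patient's event is recorded, but section 9 gives it no denominator and no listing. The study is single-arm and descriptive, so the reported percentages are its result. An event left out of the safety set is left out of that result, and what is lost would be an event of the device or of the surgery that the study is meant to describe.

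**Working it through.** **Step 1. Can an ADE occur in a screening failure?** Patient AEs are reportable only from the start of placement (section 8.3). A screening failure is a consented patient without the device (section 11.3.4). A reportable patient AE in a screening failure must therefore come from a placement that was started and not completed. Section 8.4 requires ADEs in screening failures to be followed, so the protocol provides for this case.

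**Step 2. Where would that ADE be analysed?** Sections 9.1.1 to 9.1.3 all require receipt of the implant, and section 9 adds no listing for other patients. Followed as written, the plan gives this ADE no place in the secondary endpoint.

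**Step 3. Is the case plausible in this protocol?** Section 5 describes taking the implant out during insertion because of hard bone, under-preparation or high torque, before final seating. It calls removal after full seating unlikely. Table 6 lists lack of primary stability at surgery, and aspiration or swallowing of the implant, among the expected ADEs. The case is foreseeable, but the documents give no frequency.

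**Step 4. Which cases are certain?**

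| Situation at the end of surgery | In the safety set? |
|---|---|
| Surgery started, no implant inserted | No |
| Implant seated and removed in the same session, none left in place | Unclear: *received* is not defined |
| Implant in place, stable or not | Yes |

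**Step 5. Size.** The protocol states no ADE rate, so there is no figure to reproduce. Inputs: n = 40, the planned minimum in section 3.5, and an assumed number x of patients with an ADE in the safety set. Because enrolment means receipt, an abandoned placement comes on top of the 40. One further patient with an ADE changes x/n to (x + 1)/(n + 1), a shift of (n − x)/[n(n + 1)] = (40 − x)/1640.

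| x (assumed) | Safety set as written | One added patient with an ADE | Shift, percentage points |
|---|---|---|---|
| 0 | 0/40 = 0.0% | 1/41 = 2.4% | 40/1640 = 2.4 |
| 4 | 4/40 = 10.0% | 5/41 = 12.2% | 36/1640 = 2.2 |
| 8 | 8/40 = 20.0% | 9/41 = 22.0% | 32/1640 = 2.0 |

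For scale, the exact 95% interval is 0 to 8.8% for 0/40 and 0.06 to 12.9% for 1/41, so the shift is small against the sampling uncertainty.

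**Step 6. How likely is any case?** With an assumed abandonment probability p per attempt and independent attempts, the chance of at least one in 40 attempts is 1 − (1 − p)^40. This gives 18% at p = 0.5%, 33% at 1%, 55% at 2% and 87% at 5%. These values of p are illustrative only, and not every abandoned placement would carry a reportable ADE.

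**The case against.** The safety set is coherent as it stands. It matches the meaning of enrolled in section 3.7, and it gives one denominator with a common planned follow-up for a study about the implant itself. Nothing in section 9 forbids listing events outside the set; the plan is silent on them and does not order them to be dropped. The wording in section 8.2.2 is advice on judging causality, not a collection or analysis rule. All of this stands. It does not close the gap, because the argument rests on sections 8.3, 8.4, 9.1.1 and 11.3.4, and silence leaves a collected event without a reported place.

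Three stronger readings are tempting, and the documents do not support them.

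- A reader might infer that every ADE of an abandoned placement is lost. An implant seated and then removed can fairly be read as received: section 7.18 records an implant as stable or unstable after placement, and Table 6 lists placement-day failures as expected ADEs. Section 8.3 also exempts swelling, pain or bleeding at Visit 2 when no worse than in standard treatment. That exemption applies to all patients, so the set of affected events is smaller than it first appears.
- A reader might infer that individual patient safety is weakened. Recording of AEs and device deficiencies, and the 24-hour reporting in sections 8.3.2, 8.3.3 and 8.3.5, do not depend on membership of the safety set.
- A reader might infer that the full analysis set likewise drops an implant lost before the first follow-up visit, because it admits only patients "from whom at least one follow-up measurement after baseline is available". That set is applied by intention to treat and keeps patients who end the study early, and section 7.14 already counts a removed implant as failed. This largely settles the matter, and it is no part of this point.

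**Conclusion.** The point holds in a narrow form and is minor. Where surgery was started and no implant was received, a reportable ADE is collected but has no place in ADE incidence. Where an implant was seated and removed in the same session, the text does not decide.

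Each omitted patient with an ADE is worth about 2 percentage points at n = 40. This assumes 40 patients in the safety set, between 0 and 8 of them with an ADE. The number of such patients is unknown and may be zero, in which case nothing changes. Implant survival, implant success, esthetic score and bone level are not affected.

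**What to change.** 1. In section 9.1.1, state that a patient in whom insertion of the study implant was begun counts as having received it for the safety set, including when the implant was removed in the same session.
2. For placements started without insertion of an implant, report beside the safety-set incidence the number of such patients and a listing of their AEs, ADEs and device deficiencies. Note that their follow-up ends when screening-failure status is assigned, so they are not mixed into 12-month incidence.
3. Reconcile sections 8.4 and 11.3.4 with this definition, so that a patient counted in the safety set is not also handled as a screening failure without comment.

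The cost is one definition, one count, one listing and the alignment of two sections. The data are already required: an eCRF for every consented patient (section 11.4.3), pages completed up to the visit of screening failure (section 11.3.4), and a log of devices opened but not used (section 4.5). There are two small downsides. ADE incidence may look slightly less favourable. The safety set may also differ from the number enrolled under section 3.7, so both counts should be shown.

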9.1.2 Full analysis set

The full analysis set (FAS) consists of all patients in the study, who received the study implant and from whom at least one follow-up measurement after baseline is available. This analysis will include patients regardless of any protocol deviations and/or premature termination. The primary analysis will be performed by the intent-to-treat principle with the FAS.

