6.1 Visit Windows

Patients need to be seen within the visit windows as stated in Table 3.

Table 3: Visit Days and Windows

Visit#	Visit Name	Visit Day and Window	
Visit 1	Screening	Up to 2 months before implant placement	
Visit 2	Implant Placement (Baseline)	Day 0	
Visit 3	Suture Removal	7 to 14 days after implant placement	
Visit 4	Provisional Crown 6 weeks ± 2 weeks after implant pla		
Visit 5	sit 5 Final Crown 4 months ± 1 month after implan		
Visit 6	6-month Follow-Up	6 months ± 1 month after implant placement	
Visit 7	12-month Follow-Up (Primary Endpoint)	1) 12 months ± 1 month after implant placement	

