6.4 Suture Removal (Visit 3)

At Visit 3, sutures will be removed according to the routine of the respective study center and Investigator. Usually sutures are removed 7 - 14 days after implant surgery.

The following evaluations will be performed and documented at Visit 3, which are described in details in Section 7:

- Oral hygiene assessment
- Photograph of the implant site
- Implant survival
- AEs
- Changes in concomitant medications
- Suture removal

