7.14 Implant Survival

Implant survival will be assessed at the time points listed in the schedule of assessment (Table 2).

A "surviving implant" is an implant stably inserted in the jaw. Note, that a surviving implant may not be successful if the success criteria (see Section 7.13) are not fulfilled.

A "failed implant" is an implant that:

- Has been removed; or
- Has fractured beyond repair.

[figure not shown]

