11.3.5 Early Withdrawal

Any patient may withdraw from the study any time without prejudice and will be offered an alternative treatment related to their dental condition. Patients will be advised of the need for the prescribed follow-up visits for their ongoing care and well-being.

The Investigator may withdraw any patient from the study in the case of:

- Non-compliance with the protocol
- Failure to attend the follow-up visits
- SAE or AE, which in the opinion of the Investigator prevents the patient's further participation in the study.

The Investigator must withdraw any patient from the study in the case of:

Implant loss

The patient withdrawal will be documented on a Study Termination eCRF page and must include the reason for the patient withdrawal. Withdrawn patients will not be replaced and cannot be re-enrolled.

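### Does the follow-up condition in the full analysis set let an implant lost before the first follow-up visit escape the primary survival analysis?

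*Combined protocol and SAP*

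**What the plan says.** Section 9.1.2 (protocol, Statistical Considerations) defines the FAS by two conditions: the patient received the study implant, and is one "from whom at least one follow-up measurement after baseline is available". The term is not defined further. The same paragraph adds: "This analysis will include patients regardless of any protocol deviations and/or premature termination". It ends: "The primary analysis will be performed by the intent-to-treat principle with the FAS".

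The related passages are these.

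- **First survival assessment.** Table 2 schedules survival at Visits 3 to 7. Table 3 places Visit 3 "7 to 14 days after implant placement", and section 6.4 lists survival among that visit's evaluations.
- **Failure.** Section 7.14 gives two alternative conditions. The first reads "Has been removed; or" and the second is irreparable fracture. Neither has a time limit.
- **Withdrawal.** Section 11.3.5 states "The Investigator must withdraw any patient from the study in the case of" implant loss. It continues: "The patient withdrawal will be documented on a Study Termination eCRF page and must include the reason for the patient withdrawal".
- **Recording.** Adverse event reporting starts at placement (8.3). Device effects go on the adverse event page and are followed until resolved (8.3.4, with 8.4).
- **Other sets.** The safety set (9.1.1) contains every implanted patient. The per-protocol set (9.1.3) requires Visits 1 to 7.

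**The concern.** Suppose an implant is placed on Day 0 and lost on Day 4. The loss makes the patient a failure and, through mandatory withdrawal, also ends the visits that would have supplied a scheduled assessment. If the FAS condition means a value from a scheduled visit, this patient leaves the primary analysis because of the outcome being measured, and survival can only be biased upward. The doubt is greatest when the loss is learned away from a visit, for example in the telephone call of section 11.5. The other sets would not restore it to the survival figure: the safety set serves the safety analysis, and the per-protocol set excludes the patient in any case. Table 6 lists loss before osseointegration among the expected device effects. With about 40 patients, one case could decide whether the report says 100% or 97.5%.

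**Working it through.** **Step 1: does the text exclude the patient?** Four points bear on it.

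1. The FAS condition requires that a measurement after baseline be available. It does not mention a scheduled visit or a visit window.
2. Survival is a status, not a reading on a scale. Under 7.14, establishing that the implant has been removed establishes the endpoint value, and a removal after placement is by definition after baseline.
3. That value will be on record. Loss is a listed device effect (Table 6), so it belongs on the adverse event page. The recording exemption in 8.3 is for events such as swelling, pain or bleeding of ordinary intensity. Section 11.3.5 separately requires the withdrawal reason.
4. Withdrawal for implant loss is premature termination, which section 9.1.2 says does not remove a patient. Dropping a documented failure would also contradict the intent-to-treat principle in the same paragraph.

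Exclusion therefore needs the words "from whom at least one follow-up measurement after baseline is available" to be read more narrowly than they are written.

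**Step 2: how wide is the window?** A loss found at Visit 3 is itself a survival assessment, so that patient is in the FAS on any reading. The case is confined to losses before Day 7 to 14, or later only if early visits are missed. Table 6's early loss means loss before osseointegration. The documents give no time for that, so it is not the same as loss before the first attended visit.

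**Step 3: size if the strict reading were applied.** The plan gives no derived figure to reproduce: 40 is a stated minimum (3.5) without a calculation (section 9). Inputs are 40 implants and assumed failure counts. The estimate is x/n, with x surviving implants and n patients analysed. The exact (Clopper-Pearson) 95% limits are the 0.025 quantile of Beta(x, n − x + 1) and the 0.975 quantile of Beta(x + 1, n − x). When x = n the lower limit is 0.025^(1/n) and the upper limit is 100%. The plan names no interval; these only show scale.

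| Assumed case | Loss counted | Loss dropped | Difference |
|---|---|---|---|
| No loss before the first attended visit | – | – | 0 |
| One such loss, no other failure | 39/40 = 97.5% (86.8 to 99.9) | 39/39 = 100% (91.0 to 100) | 2.5 points |
| One such loss, one later failure | 38/40 = 95.0% (83.1 to 99.4) | 38/39 = 97.4% (86.5 to 99.9) | 2.4 points |
| Two such losses, no other failure | 38/40 = 95.0% (83.1 to 99.4) | 38/38 = 100% (90.7 to 100) | 5.0 points |

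**Step 4: how likely is one case?** The chance of at least one such loss in 40 is 1 − (1 − p)^40. For assumed p of 0.5%, 1% and 2% it is 18%, 33% and 55%. These rates are assumptions. They count losses before the first attended visit, not all early failures.

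**The case for a change.** The strongest reply is that the follow-up condition stands in the sentence that defines the set, and neither the intent-to-treat phrase nor the premature-termination phrase expressly waives it. The term is undefined, no passage says that an adverse event entry or a telephone report qualifies, and one sentence fixed before the data are seen would settle the matter at almost no cost. If a known failure were dropped, the bias would have a known direction.

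Part of this stands. The definition is unwritten, and the telephone route is the least secure: section 8.4 does not follow ongoing events in patients documented as lost to follow-up. But a reported loss would still be recorded as the reason for withdrawal, and it gives the analyst the endpoint value.

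An added sentence would only state the reading that the paragraph already supports. It would also put into words an asymmetry: a patient with no attended visit enters the FAS only if the implant is known to have failed. That effect is small. With one such loss, two patients never seen again and no other failure, the FAS gives 37/38 = 97.4%. If both unseen implants had in fact survived, the full figure would be 39/40 = 97.5%, a gap of about 0.1 point.

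**Conclusion.** No change follows. This is an undefined term that an analyst would fill sensibly, because sections 7.14, 8.3.4, 9.1.2 and 11.3.5 together lead to counting a documented early loss as a failure. The strict reading would overstate survival by about 2.5 points for each such loss among 40 implants, and by nothing if none occurs. That size rests on assumed counts, since the documents give no rate, and on every other patient being followed. The plan is descriptive (section 9), with no hypothesis or threshold that the difference could alter, and the loss would appear in the safety results in any case. The conclusion assumes that sites record losses as the protocol requires. It does not extend to patients never seen after surgery for whom no failure is recorded.
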